6. STUDY PROCEDURES

Baseline Assessments and Procedures

Individuals who are interested in participating in the study will be invited to attend a Screening Visit (maximum 2 hours). Demographic information will be collected:

Age (years, months), years in full-time education

Participants' eligibility to take part will be checked by recording the following:

- Weight, height, and BMI
- Number of cigarettes smoked per day, units of alcohol consumed per week, caffeinated drinks consumed per day
- Medical history (including family psychiatric history), details of current and past medication
- Current and prior use of drugs (to exclude for drug use in the three months prior to the study)
- Menstrual cycle (in order to avoid scheduling testing in the premenstrual week)
- SCID-V interview (Structured Clinical Interview for DSM-V) to probe for current or past psychiatric illness
- Urine pregnancy test (female participants only)
- MRI screening form to ensure no contraindication to MRI scanning
- Edinburgh Handedness Inventory (see APPENDIX G: STUDY QUESTIONNAIRES)

The following baseline assessments will be completed (APPENDIX G):

- Beck Depression Inventory (BDI)
- Eysenck Personality Questionnaire (EPQ)
- State and Trait Anxiety Inventory (STAI)
- Positive and Negative Affect Schedule (PANAS)
- Snaith-Hamilton Pleasure Scale (SHAPS) a measure of anhedonia
- National Adult Reading Test (NART) a measure of verbal intelligence
- Side effect questionnaire (to determine baseline of bodily symptoms/'side effects')
- Visual Analogue Scales (VAS) measuring subjective state

Participants will be asked to wait while their eligibility to take part is assessed by a medical doctor involved in the study (maximum 30 minutes). Any participant for whom additional information is required before an eligibility judgment can be made will be asked to return on a different day once this information has been obtained.

Eligible participants will be randomised, using an online randomisation tool, to receive either seven-day prucalopride, or seven-day placebo administration. Randomisation will occur on the day of screening, or up to a maximum of four weeks after screening. Randomisation after the screening visit will occur in the event that further information is needed before determining whether participants are eligible to take part (for example, if a participant needs to follow up with details of allergies, or previous studies they have taken part in). In this

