6.1 Schedule of Assessments

	Pre-screening	Screening Visit	Scan Visit	Testing Visit
Procedures	Phone	VISIT 1	VISIT 2	VISIT 3
Send/ present PIS	Х	Х		
Eligibility assessment	Х	Х		
Written informed consent		Х		
SCID		Х		
Medical history		Х		
Physical examination		Х		
Sociodemographics		Х		
Baseline mood (BDI, SHAPS),		Х		
personality (EPQ) and cognitive				
(NART) trait measures				
Randomisation		Х		
State and Trait Anxiety Questionnaire		Х	X (BEFORE	X (BEFORE
(State and Trait form of the State-			AND	AND AFTER)
Trait Anxiety Inventory STAIS)			AFTER)	
Positive and Negative Affect		X	X (BEFORE	X (BEFORE
Schedule (PANAS)			AND	AND AFTER)
			AFTER)	
Side effect questionnaire		X	X (BEFORE	X (BEFORE
			AND	AND AFTER)
			AFTER)	
Stress test response (VAS)		Х	X (BEFORE	X (BEFORE
			AND	AND AFTER)
			AFTER)	
Facial Expression Recognition Task				Х
(FERT)				
Probabilistic learning task (PIL)				X
Auditory verbal learning task (AVLT)				X
Categorisation, recognition and recall				X
of emotional words				
Oxford Memory Test (OMT)				X
fMRI – Emotional Faces Task			X	
fMRI – Memory Task			X	
fMRI – Resting State			X	
MRI – ASL			X	
Physiological parameters, eye			X	
tracking				

^{*}To be undertaken after baseline testing;

Abbreviations: PIS = Participant Information Sheet; SCID = Structured Clinical Interview for DSM diagnoses; BDI = Beck Depression Inventory; VAS = Visual Analogue Scale; EPQ = Eysenck Personality Scale; NART = National Adult Reading Test; (f)MRI = (functional) magnet resonance imaging; ASL = Arterial Spin Labelling; OMT = Oxford Memory Test

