6.2 Objectives and Endpoints

These outcomes have been pre-registered on clinicaltrials.gov (NCT03572790). Primary outcomes are identified by bold typeface.

Objectives		Outcome measures / endpoints		
_	ate the effects of seven day e administration compared to			
Primary	Recognition of positive and negative facial expressions	Accuracy to recognise computer-based positive and negative facial expressions (anger, disgust, fear, happy, sad, surprise)		
		Misclassifications (number of responses to each facial expression category incorrectly classified as another facial expression category)		
		Reaction time to recognise facial expressions		
	Performance on Auditory Verbal Learning Task (AVLT)	Accuracy on AVLT (number of items correctly recalled across trials)		
		Number of intrusions (words incorrectly recalled) and number of repetitions (words repeated within the same trial)		
		Number of hits and false alarms in the delayed recognition test		
Secondary	Neural response to emotional faces	Blood Oxygen Level Dependent (BOLD) signal in areas including the amygdala, anterior cingulate cortex, and orbitofrontal cortex		
	Neural response to novel vs. repeated scenes	Blood Oxygen Level Dependent (BOLD) signal to scenes that have previously been seen compared to novel scenes in areas including the hippocampus and parahippocampal regions		
	Reward sensitivity as measured by the Probabilistic Instrumental Learning Task (PILT)	Amount won, amount lost, and total monetary amount earned Accuracy (correct or incorrect symbol choice) and proportion of group choosing correct symbol per trial		

Categorisation, recall, and recognition of emotional words on emotional memory	Emotional Categorisation Task (ECAT): accuracy and reaction time to classify positive and negative descriptor words
tasks	Emotional Recall Task (EREC): number of words correctly recalled (hits) and number of words incorrectly recalled (false alarms)
	Emotional Recognition Task (EMEM): accuracy and reaction time to correctly recognise positive and negative words (hits), and number of incorrectly recognised words (false alarms)
Vigilance to fearful and happy faces on the Facial Dot Probe Task (FDOT)	Vigilance scores derived from reaction time

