8.4.2.1 Primary outcomes

Facial Expression Recognition Task (FERT):

As in previous work (Harmer et al., 2004, Harmer et al., 2009), data will be analysed using repeated measures analyses of variance (ANOVAs). Group (prucalopride or placebo) will be the between-subject factor, and emotion (6 levels) will be the within-subject factor.

Auditory Verbal Learning Task (AVLT):

The number of correctly recalled words on the following trials will be calculated: List A immediate recall trials 1-5. A repeated measures ANOVA will be used to examine if there is an effect of prucalopride administration on word recall (between subject factor: group; within-subject factors: List A acquisition trial). Independent samples t-tests will be conducted to test if there is a group difference in the number of words accurately recalled after a short or long delay (List A short and long delay trials respectively, and the number of intrusions (incorrect words not present in list) and repetitions (correct words recalled more than once in the same acquisition trial) across List A acquisition trials. Independent samples t-tests will also be used to compare List B immediate recall and delayed recognition performance (number of hits and false alarms) between the groups.

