Task	Within Subject Factors	Number of Levels	Outcomes Used	Critical Contrasts Tested in the Analyses
FERT	Face Emotion	6 (Fear, anger, happy, surprise, disgust, sad)	% Accuracy Reaction time Misclassifications	Face emotion x treatment group
ECAT	Word Valence	2 (Positive, negative)	Accuracy Reaction time	Word Valence x treatment group
EREC	Word Valence Accuracy	2 (Positive, negative) 2 (Hits, false alarms)	Number of words recalled (correctly and incorrectly)	1. Word valence x treatment group 2. Word valence x accuracy x treatment group
EMEM	Word valence Accuracy	2 (Positive, negative) 2 (Hits, false alarms)	Number of words recognised (correctly and incorrectly) Reaction time	1. Word Valence x treatment group 2. Word valence x accuracy x treatment group
FDOT	Face Emotion Probe Duration	2 (Fearful, happy) 2 (Masked, unmasked)	Vigilance scores derived from reaction time	Face emotion x treatment group

				2. Face emotion x probe duration x treatment group
AVLT	/LT Trial 5 (List A acquisition tria 1-5)		Number of words recalled Number of intrusions Number of repetitions	Trial x treatment group
PILT	Trial type	2 (Win, loss)	1.Proportion of people choosing correct symbol	Trial type x treatment group
ОМТ	Trial 2 (1 probe, 3 probes)		 Proportion of correct probe selections Absolute error for probe location Reaction Time Proportion of misbinding errors 	1.Trial condition x treatment group

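### AVLT, a primary task with no pre-treatment score, is analysed without NART or gender as covariates; the tests are valid, but some precision on the group comparison may be lost

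*Protocol*

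**What the plan says.** - **NART.** Protocol section 6 lists the "National Adult Reading Test (NART) a measure of verbal intelligence" among the baseline assessments at the screening visit, with no restriction to a subgroup. Eligible participants are randomised after that assessment, so treatment cannot affect the score. The schedule in SAP 6.1 also places NART at Visit 1 only.
- **AVLT timing.** The same schedule marks AVLT at Visit 3 only. There is no score before treatment.
- **AVLT as an endpoint.** SAP 6.2 makes AVLT a primary domain. Accuracy is the number of items correctly recalled across trials; intrusions, repetitions, and recognition hits and false alarms follow.
- **AVLT analysis.** SAP 8.4.2.1 states: "A repeated measures ANOVA will be used to examine if there is an effect of prucalopride administration on word recall". The factors are "between subject factor: group; within-subject factors: List A acquisition trial". Short and long delay recall, intrusions and repetitions are compared by t-test, and "Independent samples t-tests will also be used to compare List B immediate recall and delayed recognition performance". The table of planned comparisons at the end of SAP 8.4.2.2 gives the critical AVLT contrast as "Trial x treatment group".
- **Covariates.** None is named for any behavioural analysis. The only stated use of baseline measures is a t-test between groups (protocol section 9). SAP 8.4.3.3 and 8.4.3.5 do consider gender, grey matter and segmented volume, but for imaging only. Gender is the randomisation stratifier (SAP 4.3) and is absent from the AVLT models.

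**The concern.** With 25 per group and no pre-treatment AVLT, stable differences in verbal ability between people stay in the error term of every between-group AVLT comparison, and any chance imbalance between the arms shifts the estimate. A plausible predictor is already on file and unused. The sample size was set on fear recognition accuracy in the facial expression task; no SD, effect size or power is given for AVLT. Yet it was on verbal learning and memory that the group's earlier single-dose study reported an effect (protocol section 4). At stake is a somewhat wider interval than necessary on a primary domain, and an argument about adjustment after the fact if the arms happen to differ on NART.

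**Working it through.** **The plan's own figure.** Protocol section 9 gives drug 10.64 (SD 9.77) against placebo 3.36 (SD 5.96) and power 0.9 at 25 per group.

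- Difference = 10.64 - 3.36 = 7.28.
- Pooled SD = sqrt((9.77² + 5.96²)/2) = 8.09, so d = 7.28/8.09 = 0.90.
- Two-sided alpha 0.05 (sidedness is not stated): power 0.889 by normal approximation, 0.876 by noncentral t.

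The stated 0.9 is reproduced to within rounding, but it concerns facial expression recognition and says nothing about AVLT. For AVLT I therefore assume d = 0.8 and a range of correlations.

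**Which AVLT tests can gain.** Write recall of person i on trial j as Y_ij = m_j + b·NART_i + s_i + e_ij, where s_i is the rest of the person's stable level.

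- *Group main effect.* This compares the mean (equivalently the total) over five trials. Both b·NART_i and s_i stay in the error, so removing b·NART_i helps.
- *Trial-by-group contrast.* Any trial contrast has weights c_j that sum to zero, so sum(c_j·Y_ij) = sum(c_j·m_j) + sum(c_j·e_ij). The NART term cancels. It returns only if b differs by trial, that is, if NART predicts the learning slope.
- *t-tested scores* (delays, List B, recognition, intrusions, repetitions). These are between-group comparisons and can gain, each according to its own correlation with NART.

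**Size of the gain, NART alone.** Let r be the within-group correlation of NART with the AVLT score.

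- Residual variance is multiplied by 1 - r².
- Expected cost of chance covariate imbalance is a factor 1 + 1/46 = 1.022; error df fall from 48 to 47.
- SE ratio = sqrt((1 - r²) × 1.022).
- Power is from the noncentral t with effect 0.8/(SE ratio), 25 per group, two-sided 0.05.

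| r (assumed) | 1 - r² | SE ratio | Power at d = 0.8 | Detectable d at 80% power |
|---|---|---|---|---|
| unadjusted | 1 | 1 | 0.79 | 0.81 |
| 0.1 | 0.99 | 1.006 | 0.79 | 0.81 |
| 0.2 | 0.96 | 0.990 | 0.80 | 0.80 |
| 0.3 | 0.91 | 0.964 | 0.82 | 0.78 |
| 0.4 | 0.84 | 0.926 | 0.85 | 0.75 |
| 0.5 | 0.75 | 0.875 | 0.89 | 0.71 |

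The SE breaks even where (1 - r²) × 47/46 = 1, so r = sqrt(1/47) = 0.146, about 0.15.

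**Adding gender, pessimistically.** Credit gender with no predictive value and charge it in full: factor 1 + 2/45, 46 df. Power becomes 0.78 / 0.79 / 0.81 / 0.84 / 0.88 for r = 0.1 to 0.5, and break-even moves to r = sqrt(2/47) = 0.21. The real cost should be lower, because stratified blocks of 4 keep gender nearly balanced.

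**Chance imbalance.** The SE of a difference in means of a standardised baseline trait is sqrt(2/25) = 0.283 SD. The probability of an absolute difference above 0.3 SD is 2 × (1 - Phi(0.3/0.283)) = 0.29. With r = 0.3, an imbalance of 0.3 SD moves the AVLT difference by 0.3 × 0.3 = 0.09 SD.

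**The case against.** The strongest case against is that nothing in the plan is wrong. An unadjusted analysis is a legitimate prespecified choice, randomisation makes it valid, and chance imbalance is already reflected in its standard error. Protocol section 9 would also put any NART difference on view through the baseline t-tests. All of this stands. A reader might infer that the AVLT result is biased, or that verbal ability contaminates every AVLT test. The documents support neither: allocation is random, and the contrast the SAP calls critical is within-subject, where a constant effect of NART cancels.

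A reader might also infer that precision is certainly lost. That rests on a correlation the documents do not give. Recruitment is largely through colleges, university departments and a second local university, so the NART range may be narrow and r low; below about 0.15 there is no gain. Nor do the documents show that NART is the best available predictor, since age and years of education are collected as well.

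What the objection does not remove: SAP 6.2 defines AVLT accuracy as recall across trials, which is a group main effect, and most other AVLT endpoints are plain between-group comparisons. On those, adjustment offers a possible gain for a very small possible loss, and the same SAP already contemplates covariates for imaging.

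**Conclusion.** The point holds as a modest matter of efficiency, confined to the group effect on total recall and to the AVLT scores compared by t-test. For r between 0.3 and 0.5, adjusting for NART would cut the standard error by about 4% to 12% and raise power at d = 0.8 from 0.79 to between 0.82 and 0.89. At r = 0.2 the gain is about one point of power, and at r = 0.1 the standard error rises by 0.6%. These figures assume d = 0.8, a two-sided 0.05 test, 25 complete participants per group and a linear NART effect; neither r nor d for AVLT comes from the documents. The validity of the planned tests is not in question, and the trial-by-group contrast is unaffected unless NART predicts how fast people learn.

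**What to change.** In SAP 8.4.2.1, before unblinding:

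1. For total recall over List A trials 1-5, estimate the group effect by ANCOVA with NART score and gender as between-subject terms.
2. Replace the t-tests for short and long delay, List B, recognition hits and false alarms, intrusions and repetitions by the same ANCOVA.
3. Keep the trial-by-group contrast as planned. Fitting step 1 to the total, rather than adding NART to the repeated measures model, avoids bringing in NART-by-trial terms. The comparison table also lists intrusions and repetitions under that contrast while the text assigns them t-tests; settle which applies.
4. Report every unadjusted result alongside.

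SAP 5.2 records amendments in December 2020 and October 2022 and refers to imaging analysis already begun, so the unblinding status must be checked. If the code has been broken, report the adjusted model as a labelled sensitivity analysis only.

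Cost: a few lines of SAP text, one or two degrees of freedom and no new data. If r is below about 0.15 (about 0.2 if gender predicts nothing and is charged in full), precision falls slightly: at r = 0.1 the standard error rises by 0.6% with NART alone and by at most about 1.7% with gender added (sqrt(0.99 × 47/45) = 1.017).

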As a result of this pilot work, we used a 1mg dose of prucalopride in our previous study, which was well tolerated by healthy volunteers. The main side effects reported by participants in this study were fatigue, gastrointestinal sounds, and headache, but the rate of report of these side effects was not higher in the prucalopride group compared with the placebo group. We therefore plan to use the same 1mg dose in the current study.

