- Visual Analogue Scales (VAS)

The behavioural tasks will include the Emotional Test Battery (ETB), which has previously been found to be sensitive to the effects of antidepressants, two tests of learning and memory, and a reward task (Probabilistic Instrumental Learning; PIL). The ETB involves the presentation of emotion-related words and pictures of faces with different expressions. The reward task involves repeatedly choosing between two options and there is the possibility of winning up to £10 depending on the choices made (see 'Expenses and Benefits' below). All stimuli will be presented on a computer screen and participants will be required to respond via button presses on a keyboard.

Participants will be asked to report their adherence to the seven-day administration.

At the end of the research visit, a member of the study team will ask participants to try to guess which treatment they received, as a measure of how successful the blinding was.

Sample Handling

Female participants will be required to give a urine sample for a pregnancy test at the screening visit. Urine samples will be destroyed immediately after the test result has been obtained.

Discontinuation/Withdrawal of Participants from Study

Each participant has the right to withdraw from the study at any time. In addition, the Investigator may discontinue a participant from the study at any time if the Investigator considers it necessary for any reason including:

- Pregnancy
- Ineligibility (either arising during the study or retrospectively having been overlooked at screening)
- Significant protocol deviation
- Significant non-compliance with treatment regimen or study requirements
- Withdrawal of Consent
- Loss to follow up

If a participant is withdrawn, no further procedures or observations will continue to be required. Withdrawal from the study will result in exclusion of the data for that participant from analysis. Withdrawn participants will be replaced. The reason for withdrawal if given will be recorded in the Participant Log of the Research Master File.

Definition of End of Study

The end of the study for participant involvement is the date of the last visit of the final participant.

Expenses and Benefits

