a) There is a theoretical risk that a participant may have an adverse reaction to the study drugs. Participants will be informed of the potential side effects prior to taking the medication. To minimise risk, the participants' general health will be assessed before being accepted into the study. They will be excluded from the study if they are currently taking any psychoactive medication or if they have any known contraindications to taking the drug (see exclusion criteria).

The most frequently reported adverse reactions associated with prucalopride 2mg therapy are headache (17.8%) and gastrointestinal symptoms (abdominal pain (13.7%), nausea (13.7%) and diarrhoea (12.0%)). Other side effects associated with prucalopride are decreased appetite, dizziness, vomiting, flatulence, fatigue, and gastrointestinal sounds. The terminal half-life of prucalopride is about 1 day. There is less information about the side effect profile in healthy volunteers rather than patients, or after short-term prucalopride 1mg administration, although a single 1mg dose of prucalopride was well tolerated in our previous healthy volunteer study. The potential side effects are clearly stated in the Participant Information Sheet and researchers will discuss these with participants as part of the informed consent procedure.

The drug has been tested in healthy volunteers in pharmacokinetic studies and to establish interactions with other drugs (for example, we know that prucalopride does not affect the pharmacokinetics of the oral contraceptive (9)).

To minimise the risk associated with side effects, participants will be contacted on days 2 and 4 of the study week by a named researcher to check there are no concerns. All participants will have 24-hour contact details of a named researcher who they can contact during the study period. The named researcher will in turn contact a qualified medical doctor if necessary. In order to limit the risks associated with fatigue, during the week of prucalopride/placebo administration, participants will be advised not to drink alcohol, and not to carry out activities requiring full alertness if they are aware of any impairment.

If judged necessary by the medical lead, the randomisation code will be broken for that individual by the medical supervisor and the participant will be advised to stop taking the medication and withdrawn from the study.

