9. STATISTICS AND ANALYSIS

Do you have a statistical plan?	Yes X	No 🗌
If no, please justify.		
The IBM SPSS statistical software will be use to analyse all behavioural data.		
Demographic and baseline measures will be analysed using independent t-tests.		
Mood, anxiety, and side effect measures will be analysed using repeated measures analysis of variance (ANOVA).		
Behavioural task results will be analysed using between-groups analysis of variance (ANOVA).		
Any significant interactions will be followed up using simple main effect analyses. When assumptions of equality of variances are not fulfilled, the Greenhouse-Geisser procedure will be used to correct the degrees o freedom.		
Analysis of fMRI endpoints will be completed using the FSL software package.		
Number of Participants		
50 healthy volunteers (25 per group)		

Have you done a sample size calculation?	Yes 🖂	No 🗌
If yes, please give details below		
If no, please give details to indicate you have considered the implications the selected		
sample size will have on the study outcome		
We will be using the Emotion Test Battery, which is a well validated set of emotional proces sensitive to antidepressant effects. On the facial expression recognition task, one of the magnitudes is accuracy at recognising fearful facial expressions and a sample size of 25/group power to detect changes of the magnitude of those we have seen in a previous antidepres volunteer study [drug mean 10.64 (SD 9.77) vs. placebo mean 3.36 (SD 5.96) from Harmer Psych; ref 6].	nain outcom would give sant healthy	e e 0.9 y
Analysis of Outcome Measures		
Data analysis will take place at the University of Oxford, Department of Psychiatry and will be undertaken by the research team under the supervision of the Principal Investigator. All data will be analysed using a between-groups analysis of variance (ANOVA). Analysis of fMRI endpoints will be completed using the FSL software package.		·

Withdrawn participants' data will not be included in the analysis.

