8.1 Analysis Populations

The population used for the analysis of data in this study will be:

- All randomised subjects for non-fMRI data, except for withdrawn participants who will not be included in the analysis.
- As per protocol set for fMRI data (criteria: fMRI data available). fMRI data will not be available for all participants per se depending on need to exclude / withdrawal.

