8.4.1 Demographic data and psychometric data

To assess changes in subjective mood and anxiety before and after prucalopride/placebo administration, mixed model ANOVAs will be performed with time as a within-subjects factor and group as a between-subjects factor on STAI-S, PANAS, and VAS ratings. Post hoc analyses using independent samples t tests will follow up any significant interactions. A generalised linear model will be used to analyse side effects.

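### The side-effect comparison leaves out participants withdrawn because of a reaction, and no safety set or by-arm report of withdrawals makes up for it

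*Protocol*

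**What the plan says.** **Side effects are compared between arms.** Protocol section 9: "Mood, anxiety, and side effect measures will be analysed using repeated measures analysis of variance (ANOVA"). SAP 8.4.1 names a different method: "A generalised linear model will be used to analyse side effects". Neither gives this analysis a population of its own.

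**A reaction can lead to withdrawal.** Protocol section 8d, on the risk of an adverse reaction, says that where the medical lead thinks it necessary the code is broken and "the participant will be advised to stop taking the medication and withdrawn from the study".

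**Withdrawal removes the data.** Protocol section 6 (Discontinuation/Withdrawal): "Withdrawal from the study will result in exclusion of the data for that participant from analysis. Withdrawn participants will be replaced". Protocol section 9 repeats the rule: "Withdrawn participants' data will not be included in the analysis". SAP 8.1 defines the main population as "All randomised subjects for non-fMRI data, except for withdrawn participants who will not be included in the analysis", and SAP 8.2 has the same exclusion as its only missing-data rule. The side-effect questionnaire is non-fMRI data, so it is covered. Replacement is stated in the protocol only.

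**Nothing more is collected.** Protocol section 6: "If a participant is withdrawn, no further procedures or observations will continue to be required". The reason for withdrawal goes into a participant log, if one is given.

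**The concern.** A reaction is one route to withdrawal, and withdrawal removes the participant from the analysis that counts reactions. Exclusion then depends on the outcome being measured. If it happens more often on drug, the side-effect rate on drug and the difference from placebo are both too low. Because withdrawn participants are replaced, each arm can still be reported at its planned 25, and the loss need not show in the denominators.

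What is at stake is the tolerability statement. The protocol's synopsis shows how such a statement is used. It supports the choice of dose partly by noting that in the previous single-dose study "the rate of report of these side effects was not higher in the prucalopride group compared with the placebo group". Protocol section 8d also says that there is less information on side effects in healthy volunteers and after short-term 1mg use, so this comparison would add to a small body of evidence.

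**Working it through.** **1. The plan's own figures.** The documents give no expected withdrawal rate and no expected side-effect rate at 1mg, so there is no figure on this point to reproduce. The nearest design figure is the power of 0.9 with 25 per group in protocol section 9. The difference is 10.64 − 3.36 = 7.28. The pooled SD is √((9.77² + 5.96²)/2) = 8.09. By the normal approximation with two-sided 0.05, the power is Φ(7.28/(8.09 × √(2/25)) − 1.96) = Φ(1.22) = 0.889. It reproduces, and nothing below depends on it.

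**2. Does any other provision bring the withdrawn participants back?**

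| Provision | What it does | Restores them to the comparison? |
|---|---|---|
| SAP 7.2, analysis of all randomised subjects with data for a task | Governs exclusion task by task during data cleaning | No; SAP 8.1 and 8.2 still apply |
| Protocol 8b, serious adverse events | Case-by-case reporting if judged related and unexpected | No; expected, non-serious reactions do not reach it |
| Protocol 6, participant log | Records a reason, if given | No; no by-arm report is planned |
| Protocol 6 and 8c, calls on days 2 and 4 | Check for concerns | No; no side-effect form is specified at these calls |

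**3. When is the form completed?** Protocol section 6 gives the side-effect questionnaire at screening and then before and after testing on days 6 and 7. Someone withdrawn before day 6 has only the screening form. Removing the exclusion rule alone would therefore add no on-treatment record for that person.

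**4. Illustration of size.** Let p be the true rate on drug and w the share of affected participants who are withdrawn. Assume that nobody without the side effect is withdrawn. A fraction p(1 − w) stays with the side effect, and 1 − pw stays in total, so

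analysed rate = p(1 − w) / (1 − pw).

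Replacements drawn from the same population under the same rule leave this expectation unchanged, so the formula is the same with or without replacement. The number to be randomised to reach 25 analysed is 25/(1 − pw).

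Take p = 12.0%, the diarrhoea rate that protocol section 8d gives for 2mg. It is not a rate at the study dose. The values of w are assumed.

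| w | Analysed rate | Randomised for 25 analysed |
|---|---|---|
| 10% | 0.108/0.988 = 10.9% | 25/0.988 = 25.3 |
| 25% | 0.090/0.970 = 9.3% | 25/0.970 = 25.8 |
| 50% | 0.060/0.940 = 6.4% | 25/0.940 = 26.6 |

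**5. What happens to the comparison?** If p and w were the same in both arms, both rates would fall equally and a true null difference would stay null. The comparison is distorted only if the product pw, the rate of reaction-driven withdrawal, differs between arms.

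**The case against.** Several objections have force.

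- **Withdrawal is discretionary.** A participant is withdrawn after a reaction only if the medical lead thinks it necessary. The questionnaire in Appendix G grades each item from absent to severe, so affected participants who continue are analysed. A reader might infer that only people who tolerated seven days are compared, or that all the worst cases on drug vanish. The documents support neither. What is missing is those actually withdrawn.
- **The rule applies to both arms.** Excess withdrawal on drug is plausible, because the documents list gastrointestinal reactions to prucalopride and two of three pilot participants had diarrhoea after 2mg. There is no figure for it at 1mg. The only 1mg comparison described, after a single dose, found no excess of side effects on drug.
- **The illustration is loose.** The rate comes from 2mg and the withdrawal shares are assumed. The form asks about current symptoms and is given late in treatment, so it does not measure incidence over the week.
- **The comparison is weak in any case.** With 25 per arm, Fisher's exact test of 12% against an assumed 4% on placebo has about 3.5% power with nobody excluded. The exclusion would rarely change a significance test. It would change the reported rates.
- **Side effects are not a primary, secondary or tertiary outcome,** and the synopsis says the study is not designed to identify adverse reactions.

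Two further readings also go too far. Nothing shows that the previous study excluded withdrawn participants, so its result cannot be called biased on this ground. Replacement does not enlarge the bias; it only hides the loss.

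All of this limits the size and priority of the point. It does not remove the defect: both documents plan the comparison, and their written rules take people out of it because of what it measures.

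**Conclusion.** The concern holds in limited form. As written, the side-effect comparison covers only participants who were not withdrawn, and no safety set or by-arm report of withdrawals shows who is missing. That conclusion follows from the text and needs no assumed rate.

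The direction does need an assumption. Side effects on drug are understated relative to placebo only so far as reaction-driven withdrawals are more frequent on drug. The size is unknown. The range of 10.9% to 6.4% for a true 12% illustrates the mechanism and does not predict this trial's result. If nobody is withdrawn for a reaction, the effect is nil.

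This is a reporting and analysis-population correction for an unranked but planned analysis. The primary task endpoints, the fMRI endpoints and the power statement are not affected by this point.

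**What to change.** 1. **SAP 8.1 and 8.2:** define a safety set of all randomised participants who took at least one capsule. Include data from withdrawn participants up to last contact, unless they ask for removal. State in SAP 8.4.1 that the side-effect model uses this set.
2. **Protocol sections 6 and 9:** limit the exclusion of withdrawn participants' data to the task and fMRI endpoints.
3. **Report by arm** the numbers randomised, withdrawn and unblinded, with reasons, and show side effects as a separate reason. This is the essential part, because a new analysis set alone adds no on-treatment form for anyone withdrawn before day 6.
4. **If data collection is still open,** complete the existing side-effect form when a participant stops. SAP 5.2 refers to an October 2022 upload and SAP 8.3 describes capsule supply in the past tense, so this may no longer be possible. In that case rely on the logged reasons.

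The cost is amended wording in both documents, one by-arm table and, where still feasible, one short extra form at stopping. Forms will be incomplete for early withdrawals, and the reported side-effect rate on drug may look less favourable. The consent wording was not available for this review, so what participants were told about data already collected should be checked before withdrawn data are used.
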